### **1.6 Statistical Methods for Primary Analysis**

The primary hypothesis test will compare the proportions achieving HIV viral suppression at 12 months across the three study groups. Death from any cause will be considered equivalent to non-suppression for the purposes of calculating this proportion. (Differences in outcome when deaths are categorized with respect to likelihood of being HIV and/or drug use related will be explored in a secondary analysis.) All treatment comparisons will be performed under the Intent-to-Treat (ITT) criterion in the sense that participants will be analyzed in the arm to which they were randomized, regardless of subsequent events. However, participants who are lost to follow-up before 6 months will not contribute to the primary analysis. A Generalized Estimating

Equations (GEE) model will be employed (Zeger & Liang, 1986) with a binomial distribution and logit link as implemented in SAS. The GEE model will include both 6-month and 12-month HIV viral suppression status. However, the primary test of the hypothesis will be based on contrasts involving the 12-month proportions only. This model gains statistical power by pooling the error term across the two follow-up times and is closer to an ITT approach than would be the analysis of 12-month events only. It does not impute data that are missing at month 12 with the exception of death, which will be considered equivalent to non-suppression. Any potential correlation between patients within a site will be controlled by estimating a fixed effect for site in this model.

A simple closed-testing procedure (Westfall, Tobias, Rom, Wolfinger, & Hochberg, 1999) will be used to control family-wide type I error at 0.05 while still allowing all three pairwise comparisons between arms. Specifically, let  $P(123)$  be the (two-sided) p-value of the contrast testing equality among all three arms, while  $P(12)$ ,  $P(13)$ , and  $P(23)$  are the (two-sided) p-values for arms 1&2, 1&3, and 2&3, respectively. Then, let the adjusted p-value for the (1,2) comparison be

$$P^*(12) = \max[P(123), P(12)]$$

and similarly for the other pairwise comparisons. Tests of pairwise equality will be performed by comparing  $P^*(12)$ ,  $P^*(13)$ , and  $P^*(23)$  to the 0.05 level of significance.

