## 1.7 Rationale for Sample Size and Statistical Power

Power calculations were based on a simulation of several scenarios, with 5000 iterations per scenario. In each iteration, 266 virally unsuppressed participants were recruited to each of three treatment groups, after which death and dropout rates, and rates of suppression before and after 6 months, were imposed so as to result in proportions of simulated participants dead, lost, suppressed, and unsuppressed at both 6 and 12 months as indicated below. These rates characterized the scenario. (Note that the rates dictate the probabilities of joint occurrences of outcomes at 6 and 12 months, but it is possible for more than one set of rates to produce the same set of 6-month and 12-month margins.)

Once these data were simulated, they were subjected to a Generalized Estimating Equation (GEE) analysis in which dropouts were ignored and dead participants were combined with unsuppressed participants. More specifically, the GEE regressed state (suppressed versus unsuppressed or dead) on time (6 months, 12 months), treatment group (Patient Navigator = PN, Contingency Management + Patient Navigator = CM, Treatment as usual = TAU) site (1-10) and the time by treatment group interaction using a binomial link. The outcome of interest was the proportion suppressed (versus unsuppressed or dead) in each arm at 12 months, but the analysis incorporated 6-month data so that the 6-month/12-month correlation could in part offset loss to follow-up between 6 and 12 months. Contrasts were used to obtain p-values for the hypotheses CM=PN=TAU, CM=PN, CM=TAU, and PN=TAU with respect to the outcome of interest.

These p-values were combined together using the closed-testing methodology explained in Section 1.6. Note was taken of which of the pairwise hypotheses were rejected ( $\alpha = 0.05$ , two-tailed), and which accepted according to the Closed testing algorithm in each iteration. Finally, the power for the tests of the various hypotheses was estimated as the proportion of the 5000 iterations in which each hypothesis was rejected.

The scenarios were defined by the following parametric values, which varied from treatment group to treatment group:

- M6 = target suppressed proportion at 6 months (assuming no death or dropout)
- M12 = target suppressed proportion at 12 months (assuming no death or dropout)
- S = Probability that a participant will be suppressed at 12 months, given he was suppressed at 6 months

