- U = Probability that a participant will be unsuppressed at 12 months, given that he was unsuppressed at 6 months
- E = quarterly probability of death for a suppressed participant
- F = quarterly probability of death for an unsuppressed participant
- G = quarterly dropout probability for a suppressed participant
- H = quarterly dropout probability for an unsuppressed participant

Four scenarios (A-D) were investigated, with parametric values given by the table below:

Scenario	Group	M6	M12	S	U	E	F	G	H
A	TAU	0.18	0.16	0.95	0.99	0.02	0.05	0.04	0.04
A	PN	0.375	0.26	0.85	0.99	0.02	0.05	0.04	0.04
A	CM	0.55	0.4	0.85	0.98	0.02	0.05	0.04	0.04
B	TAU	0.175	0.16	0.98	0.99	0.015	0.03	0.03	0.03
B	PN	0.33	0.24	0.94	0.98	0.015	0.03	0.03	0.03
B	CM	0.49	0.44	0.96	0.98	0.015	0.03	0.03	0.03
C	TAU	0.175	0.16	0.98	0.99	0.02	0.05	0.04	0.04
C	PN	0.33	0.24	0.94	0.98	0.02	0.05	0.04	0.04
C	CM	0.49	0.44	0.96	0.98	0.02	0.05	0.04	0.04
D	TAU	0.18	0.16	0.95	0.99	0.015	0.03	0.03	0.03
D	PN	0.375	0.26	0.85	0.99	0.015	0.03	0.03	0.03
D	CM	0.55	0.4	0.85	0.98	0.015	0.03	0.03	0.03

The numerical values of the parameters selected in scenarios A-D were chosen to match prior experience of the investigators and data from the literature. Out of care HIV-infected individuals who are admitted to the hospital will have very low rates of viral suppression, in the range of 10-15%. From clinical discussions amongst the research team it was decided that a 10% to 12% increase (i.e., moving from 15% to 25% or 15% to 27%) is a minimally clinically meaningful change. We therefore aimed power determination at uncovering around a 12% pair-wise difference between intervention conditions. From an ongoing study of [name] and [name], a 12-15% death rate seemed to be likely in this cohort. Finally, since all participants are heavy drug and/or alcohol users it is appropriate to account for 10-15% attrition (in addition to the deaths) in these calculations even though, the research team has a history of achieving high rates of follow-up.

Power results are given in the following table, along with the parametric value of M12 and simulated resulting proportions of death, attrition, and suppression ignoring dropouts. Across each of the 4 scenarios, there is 87% power or greater to reject any of the 3 pair-wise comparisons under the assumptions set forth and a sample size of 266 study participants per treatment group.

Scenario	12-Month Statistics (percent)														

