	Observed Attrition			Observed Death			Target Suppression(M12)			Realized Suppression			Power		
	TAU	PN	CM	TAU	PN	CM	TAU	PN	CM	TAU	PN	CM	TAU vs PN	PN vs CM	TAU vs CM
A	14	14	14	16	15	14	16	26	40	16	29	42	93	87	100
B	11	11	11	10	10	9	16	24	44	17	30	44	94	92	100
C	14	14	14	16	15	14	16	24	44	16	28	42	93	89	100
D	11	11	11	10	10	9	16	26	40	16	30	44	94	89	100

\* Realized Suppression Outcome = suppressed / (suppressed + unsuppressed + dead)

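### SAP section 1.7: the tabled transition rates do not give the tabled 12-month targets, so the 93–94% power for Navigator vs usual care applies to realized differences of 12–14 points, not to the 8–10 point targets

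*SAP*

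**What the plan says.** Section 1.7 describes a simulation in which "266 virally unsuppressed participants were recruited to each of three treatment groups". Each scenario row lists "M6 = target suppressed proportion at 6 months (assuming no death or dropout") and "M12 = target suppressed proportion at 12 months (assuming no death or dropout"). It also lists S, the chance of staying suppressed from month 6 to month 12, and U, the chance of staying unsuppressed. Quarterly death (E, F) and dropout (G, H) rates complete the row.

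The section names a rise from 15% to 25% or from 15% to 27% as the smallest clinically meaningful change, and continues: "We therefore aimed power determination at uncovering around a 12% pair-wise difference between intervention conditions". The results table prints the M12 target beside a realized proportion, footnoted as "Realized Suppression Outcome = suppressed / (suppressed + unsuppressed + dead"). It reports power of 93/94/93/94% for TAU vs PN in scenarios A to D, 87/92/89/89% for PN vs CM, and 100% for TAU vs CM. The text concludes: "Across each of the 4 scenarios, there is 87% power or greater to reject any of the 3 pair-wise comparisons under the assumptions set forth".

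Section 1.6 sets the test: a closed procedure "to control family-wide type I error at 0.05 while still allowing all three pairwise comparisons between arms", with two-sided p-values.

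**The concern.** The scenario table specifies the 12-month margin twice, once as M12 and once through M6, S and U, and the two specifications disagree. The reader cannot tell which effects the printed power belongs to, and the text does not mention the discrepancy.

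This matters most for TAU vs PN, one of the three primary hypotheses. Read against the target column, the table promises 93–94% power for differences of 8 to 10 points, and a null result would then look more conclusive than it is. Section 1.8 also plans a conditional power analysis for futility without naming the effect to be used. If the design effect were taken from section 1.7, two candidates would be available.

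**Working it through.** **Inputs (all from SAP section 1.7).** 266 per arm; M6, M12, S, U, E, F, G and H from the scenario table; attrition, death, realized suppression and power from the results table. The two-sided 0.05 level and the closed test come from section 1.6.

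**1. The identity.** With no death or dropout, M12 = M6×S + (1−M6)×(1−U).

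| Scenarios, arm | M6×S | (1−M6)×(1−U) | Implied M12 | Stated M12 |
|---|---|---|---|---|
| A, D TAU | 0.18×0.95 = 0.1710 | 0.82×0.01 = 0.0082 | 0.179 | 0.16 |
| A, D PN | 0.375×0.85 = 0.3188 | 0.625×0.01 = 0.0063 | 0.325 | 0.26 |
| A, D CM | 0.55×0.85 = 0.4675 | 0.45×0.02 = 0.0090 | 0.477 | 0.40 |
| B, C TAU | 0.175×0.98 = 0.1715 | 0.825×0.01 = 0.0083 | 0.180 | 0.16 |
| B, C PN | 0.33×0.94 = 0.3102 | 0.67×0.02 = 0.0134 | 0.324 | 0.24 |
| B, C CM | 0.49×0.96 = 0.4704 | 0.51×0.02 = 0.0102 | 0.481 | 0.44 |

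M6×S alone exceeds M12 in every row, so no value of U between 0 and 1 reconciles them. Rounding is not the explanation.

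**2. Cross-check in the results table.** Deaths count as failures, and dropout does not depend on suppression (G = H). The suppressed who remain are at most M12×(1−G)^4 of those randomized. The denominator is at least (1−G)^4, because the dead cannot later drop out. Realized suppression therefore cannot exceed M12. The printed values exceed it in 7 of 12 cells. For PN they are 29, 30, 28 and 30 against targets of 26, 24, 24 and 26.

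**3. Reproducing the printed figures from S and U.** The SAP does not say how the quarterly rates attach to suppression status. The closest match applies the unsuppressed rates in quarter 1, the 6-month status in quarters 2 and 3, and the 12-month status in quarter 4. Power comes from 2,000 simulated trials per scenario: GEE with exchangeable correlation, robust Wald tests, the closed test, no site term.

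| Scenario | Realized TAU/PN/CM, computed | Printed | TAU vs PN power, computed (printed) | PN vs CM power, computed (printed) |
|---|---|---|---|---|
| A | 15.7/28.5/41.8 | 16/29/42 | 94 (93) | 86 (87) |
| B | 16.5/29.7/44.2 | 17/30/44 | 93 (94) | 92 (92) |
| C | 15.7/28.3/42.2 | 16/28/42 | 93 (93) | 89 (89) |
| D | 16.4/29.9/43.8 | 16/30/44 | 95 (94) | 90 (89) |

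Agreement is within about 1 point, so the printed power came from S and U. The printed realized differences are 13/13/12/14 points for TAU vs PN and 13/14/14/14 for PN vs CM. The target differences are 10/8/8/10 and 14/20/20/14.

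**4. Power if M12 is met.** Solve S = [M12 − (1−M6)(1−U)]/M6 and leave everything else unchanged. For PN, S falls from 0.85 to (0.26−0.00625)/0.375 = 0.68 in A and D, and from 0.94 to (0.24−0.0134)/0.33 = 0.69 in B and C. Under the timing in step 3, realized TAU and PN become 14.0 and 22.8 (A), 14.7 and 22.0 (B), 14.0 and 21.0 (C), 14.7 and 23.9 (D), which is 7 to 9 points apart.

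- TAU vs PN, GEE simulation over two timings: A 71–72%, B 56–57%, C 54–55%, D 76%.
- TAU vs PN, two-proportion formula, same timings: about 69–71%, 54–56%, 51–53% and 72–74%.
- PN vs CM: about 84–99% across scenarios and methods. TAU vs CM: about 100%.

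**5. The plan's own benchmarks.** Analysable per arm, deaths retained: 266×0.86 = 229, 266×0.89 = 237, and about 240 at 10% attrition. Power = Φ{[d − 1.96√(2p̄(1−p̄)/n)] / √([p1(1−p1)+p2(1−p2)]/n)}, where d is the difference and p̄ the mean proportion.

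- 15% vs 25%, n = 229: (0.10 − 1.96×0.03738)/0.03709 = 0.72, power 76%. At n = 240, 78% (79% with unpooled variance).
- 15% vs 27%, n = 229: (0.12 − 1.96×0.03807)/0.03765 = 1.21, power 89%. At n = 240, 90%.

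**The case against.** The strongest reply is that the power column is right for what was simulated. Realized suppression is printed and defined beside M12, so the powered effects are on the page. They are also close to the stated aim of about 12 points: scenario C shows 16% vs 28%, a 12-point difference, with 93% power. On this view only the M12 column is wrong.

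Much of this stands, and it rules out three stronger readings:

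- A reader might infer that all the printed power rests on inflated effects. For PN vs CM the realized differences (13–14 points) are equal to or smaller than the target differences (14–20), and the 87% floor is itself a PN vs CM figure.
- A reader might infer that the trial is underpowered for its aim. The 15% to 27% benchmark has 89–90% power. The 51–76% figures concern M12 differences of 8 to 10 points, which fall to 7–9 points once deaths count as failures, below the stated minimum of 10–12.
- A reader might infer that 51–76% is the trial's true power for TAU vs PN. That holds only if M12, rather than S and U, was the intended input. The SAP does not say which was, and it describes all the parameter values as chosen from experience and literature.

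Two points survive. M12 is a listed scenario parameter, so the assumptions as set forth are contradictory and the mismatch goes unexplained. And the 87% floor does not reach the 10-point change that the SAP itself calls meaningful.

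**Conclusion.** The point holds in limited form. All 12 scenario rows are internally inconsistent, and the printed power belongs to S and U. For TAU vs PN, 93–94% applies to realized differences of about 12–14 points. At the M12 differences of 8–10 points, power is about 51–76% depending on scenario and method. PN vs CM and TAU vs CM are not materially affected. The 87% floor covers the 12-point benchmark (about 89–90%) but not the 10-point one (about 76–79%).

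The inconsistency is plain arithmetic and needs no assumption. The power figures rest on an assumed timing of the quarterly rates, omission of the site term, and re-solving S alone to meet M12. Four timings led to the same conclusion; the least favourable, which fits the printed table less well, gives 49% by formula in scenario C. Simulation error is about 1 point (√(0.55×0.45/2000) = 0.011). The benchmark figures in step 5 ignore the closed test's global step and the 6-month data.

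**What to change.** Reconcile the scenario table in section 1.7 in one of two ways:

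- Replace M12 with the values S and U generate (TAU/PN/CM 0.179/0.325/0.477 in A and D, 0.180/0.324/0.481 in B and C). The printed power then stands.
- Or change the rates so that the stated M12 is met, and re-run. TAU vs PN power then drops to roughly 51–76%.

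In either case, replace the 87% sentence with one that ties each power to the realized difference it applies to. With the current rates these are 93–94% for TAU vs PN at 12–14 points, 87–92% for PN vs CM at 13–14 points, and 100% for TAU vs CM at 26–28 points. Add that a change from 15% to 25% has only about 76–79% power. If the futility analysis in section 1.8 is to use a design effect, say which.

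The cost is SAP wording and, under the second option, one re-run of the simulation. The sample size, endpoint, model and alpha do not change. The only downside is a less favourable power statement.

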### 1.8 Interim Analyses

If recruitment goes as planned, which originally was to enroll 800 participants over a 10 month period (80 participants/month), no interim efficacy or futility analyses will be done, as recruitment will be completed before any participants will have reached 12 months of follow-up, the period at which the primary outcome is measured. However, if the recruitment period becomes protracted to a point where, over a 26-month period, the number enrolled is 23.5 participants per month or slower (i.e., about 600 participants or fewer at 26 months), we will perform efficacy and futility analyses for DSMB and NIDA review. For these analyses, a two-sided, symmetric O'Brien-Fleming (1979) type boundary using the flexible Lan-DeMets (1983) procedure will be implemented for group sequential testing for efficacy, and a conditional power analysis (Jennison & Turnbull, 2000) will be implemented for futility. The threshold of 23.5 participants per month over 26 months was selected because this corresponds to an approximate point in time when 288 participants (approximately 40% of the targeted sample size after accounting for 10% attrition) will be available for 12-month outcome analysis, and approximately 600 of the targeted participants will have been enrolled (achieving 75% of the targeted sample size). Therefore, if a conclusion is reached based on efficacy or futility to stop the trial early, approximately 200 participants would not need to be enrolled into the trial. If the recruitment rate is higher than 23.5 participants per month at 26 months, i.e., if recruitment is expected to take less than 34 months, no interim analyses will be performed. Further, there is no scenario for which sample size re-estimation will be necessary. In addition, safety interim looks will be performed (without formal statistical testing) at the regular DSMB meetings or at unscheduled times per the DSMB's request.

### 1.9 Secondary Endpoints and Analyses

Secondary outcomes are divided into those related to HIV and those related to substance use. Note that the date of randomization is the time point from which all outcomes will be measured.

#### 1.9.1 HIV Related Secondary Outcomes

The data associated with the HIV secondary outcomes include binary (Yes/No), count and continuously distributed data. In the following list of HIV secondary outcomes the expected distribution is in parenthesis:

- a) Repeat primary analysis with the addition of a treatment interaction with viral suppression status at baseline (binary)

- b) Viral suppression at 12 months or HIV-related deaths (binary, note that non-HIV related deaths would be classified as missing in this analysis)
- c) Viral suppression at 6 months (binary)
- d) CD4 Cell count (continuous at 6 and 12 months)
- e) Engagement into care (visit constancy, a repeated binary at 3-month intervals)
- f) HIV care visit attendance (count)
- g) Medication Adherence (count)
- h) Hospitalizations (count)
- i) All cause mortality (binary)

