#### 1.10.1 Tests of the Secondary Outcomes

Each of the stated secondary outcomes listed in Section 1.9 will be tested separately, using the closed testing procedures described for the primary outcome to control family-wide type I error. The statistical methods used will also mirror the methods used for the primary hypothesis. Those secondary outcomes that are binary will be tested as described for the primary hypothesis using a logistic regression; whereas those secondary outcomes that involve either continuous or ordinal variables will utilize the appropriate distribution and link function. Note that the exact method of analysis will depend on the realized distribution of the particular outcome in this trial for example, an expected count data variable may need to be modeled using a zero-inflated Poisson Regression rather than a Poisson regression if there are too many zero observations to fit the standard Poisson. If there is over-dispersion, a negative binomial (or zero-inflated negative binomial) regression may be appropriate. The hypothesized

moderator variables (for viral suppression: psychological distress, housing instability, food insecurity, health literacy, HIV-related cognitive function, renal function and liver function; and CD4 count. Drug Use moderator: readiness for treatment and HCV status) will be addressed in the same way that the covariates for the planned sensitivity analysis of the primary outcomes (site, age at baseline, race and ethnicity, gender, and primary type of drug use [IV vs. non-IV, opiate vs. non-opiate, and stimulant vs. non-stimulant], baseline level of viral load) will be addressed. Models will be estimated with main effects for these variables, a main effect for randomization group and an interaction between the particular variable and randomized group on the primary outcomes. For these analyses, the overall Type I error will not be controlled, rather, the reader of any resulting journal article will be alerted to the fact that these analyses were the result of *post-hoc* exploratory analyses, and that any statistically significant results may have resulted from a Type I error, and require replication.

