### **1.13 Missing Data and Dropouts**

Missing data are a ubiquitous problem in substance use research, primarily due to dropping out and refusal. Missing data can lead to biased estimates and reduction of power, affecting the generalizability of the study. We will make every effort to minimize the amount of missing data and in the primary analyses we will include only participants with available data at 6 or 12 months, although study participants who have died will be considered a failure and not meeting virologic suppression. In all cases missingness patterns will be identified and analyses will be conducted to determine if there is differential non-death attrition by treatment arm, and if missingness is related to any of the covariates. In the case that covariates predict missingness, the data are called “Missing at Random,” (MAR) (Little & Rubin, 1987). GEE analyses are only appropriate if data are “Missing Completely at Random,” which means that no covariates predict the occurrence of missing data. Under the MAR assumption, the multiple imputations procedure can be used to fill in the data without artificially compressing the variance associated with the imputed data (Schafer, 1997). Therefore, if observed covariates predict the existence of missing data, multiple imputation will be used in a secondary analysis of the primary outcome to assess the effects of missingness on the reported results. If nonrandom missingness is of concern (Missing not at Random, MNAR), this problem will be addressed by applying pattern-mixture, propensity score or related models so that the effect of bias can be assessed in sensitivity analyses.

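### Binary all-cause mortality, tested by the primary's rule, counts deaths but omits living participants who are lost; levels are modestly overstated, and the comparison shifts only if dropout differs by arm

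*SAP*

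**What the plan says.** Item (i) of SAP 1.9.1 is "All cause mortality (binary", with no time-to-event definition, censoring rule or denominator. The analysis comes from 1.10.1: "The statistical methods used will also mirror the methods used for the primary hypothesis", and "Those secondary outcomes that are binary will be tested as described for the primary hypothesis using a logistic regression".

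The primary method is described in two places. Section 1.6 says "participants who are lost to follow-up before 6 months will not contribute to the primary analysis", and says of the GEE model: "It does not impute data that are missing at month 12 with the exception of death". Section 1.13 adds "in the primary analyses we will include only participants with available data at 6 or 12 months", with deaths counted as failures. The footnote to the power table in 1.7 shows the same denominator in use: "Realized Suppression Outcome = suppressed / (suppressed + unsuppressed + dead". The dead are in it and the lost are not.

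Section 1.9 also states that "the date of randomization is the time point from which all outcomes will be measured". Section 1.13 promises to examine differential non-death attrition by arm, but names multiple imputation only for the primary outcome.

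**The concern.** For viral suppression, a lost participant's status is simply unknown. For mortality, whether a participant is analysed depends on the outcome. Someone who dies at month 4 counts as a death, whereas someone last seen alive at month 4 is left out. Loss therefore removes only people last known to be alive, which raises the reported mortality, and raises it more where loss is greater. Event-free time up to last contact is discarded, although outcomes are timed from randomization.

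The SAP expects 12-15% deaths and a further 10-15% attrition, so about as many participants may be lost as die. Two of the three arms receive navigation sessions, so unequal retention is conceivable. The mortality comparison would then partly reflect retention.

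**Working it through.** **Inputs.** From SAP 1.7: 266 per arm; quarterly death probability 0.015-0.02 (suppressed) or 0.03-0.05 (unsuppressed); quarterly dropout 0.03 or 0.04, equal in all arms; two-sided 0.05. My assumptions: one constant death probability d per arm, and any dropout g that differs by arm.

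**1. The SAP's own figures (scenario A, TAU).** I take everyone as unsuppressed to month 6, 18% suppressed afterwards, and dropout before death within each quarter.
- Deaths by quarter: 0.0480 + 0.0438 + (0.0327 + 0.0029) + (0.0299 + 0.0027) = 16.0%. Attrition is 14.0%. The SAP states 16% and 14%.
- Mortality without dropout: 1 − 0.95² × (0.82 × 0.95² + 0.18 × 0.98²) = 17.6%.
- Lost left out: 16.0/(100 − 14.0) = 18.6%, too high by 1.0 point. Lost counted as alive: 16.0%, too low by 1.6 points.

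**2. Level under equal dropout.** Let r = (1 − d)(1 − g).
- True mortality: 1 − (1 − d)⁴.
- Still in contact and alive at 12 months: A = r⁴.
- Deaths seen: D = d(1 − r⁴)/(1 − r) if death precedes dropout within a quarter, and (1 − g) times that if dropout comes first.
- Reported mortality: D/(D + A).

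With d = 0.045 the true value is 16.8%. For g = 0.04, r = 0.9168 and A = 0.7065. D is 0.1588 (death first) or 0.1524 (dropout first), so the report is 18.4% or 17.7%. For g = 0.03 it is 17.9% or 17.5%. The excess is 0.7 to 1.5 points, the same in each arm, so a null difference stays at zero.

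**3. Equal mortality (d = 0.045), unequal dropout.** The two-sample test has nᵢ = 266(Dᵢ + Aᵢ). Its rejection rate is Φ((Δ − 1.96s₀)/s₁) + Φ((−Δ − 1.96s₀)/s₁), where Δ is the false difference, s₀ the pooled and s₁ the unpooled standard error.

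| Quarterly dropout | Event order | Reported mortality | False difference | Type I error |
|---|---|---|---|---|
| 3% vs 4% | dropout first | 17.50 vs 17.74% | 0.24 | 5.1% |
| 3% vs 4% | death first | 17.95 vs 18.35% | 0.40 | 5.1% |
| 3% vs 5% | dropout first | 17.50 vs 17.99% | 0.49 | 5.2% |
| 3% vs 5% | death first | 17.95 vs 18.76% | 0.81 | 5.6% |
| 2% vs 6% | dropout first | 17.27 vs 18.25% | 0.98 | 5.9% |
| 2% vs 6% | death first | 17.56 vs 19.19% | 1.63 | 7.4% |

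The last pair means about 7% vs 20% lost at 12 months. Log-rank stays at about 5% in simulation.

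**4. Real difference (5% vs 3% deaths per quarter; true 18.5% vs 11.5%).** With dropout 2% vs 6%, power is 68-75% if the arm with more deaths also loses more (reported 20.1 vs 11.8% or 21.1 vs 12.0%). It is about 42-49% if that arm loses fewer (19.0 vs 12.5% or 19.4 vs 13.2%). The ranges cover event order and simulation variation. Log-rank gives 58-60% either way. With 4% dropout in both arms, the binary test and log-rank both give 58-60%.

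**5. Lost counted as alive.** With d = 0.045 and dropout 6% vs 2%, the reports are 14.5 vs 16.0% or 15.4 vs 16.3%. The arm with more loss now looks safer.

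**6. Two-time GEE mirrored in full.** Participants lost after month 6 keep a 6-month row. At d = 0.04 (true 15.1%) and dropout 6% vs 2%, 150 simulated trials gave 16.6% vs 15.4%, against 17.2% vs 15.7% for the simple proportion. The bias shrinks but remains.

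**7. Life table with the lost censored at last contact.** At d = 0.04 it gives 15.1% for every dropout rate from 2% to 6%, if censoring is independent of death.

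**The case against.** The denominator is inferred. The exclusion sentences in 1.6 and 1.13 speak of the primary analysis, which needs a blood sample; vital status does not need a visit. Section 1.10.1 carries over methods and does not expressly carry over the analysis set. An analyst could use everyone with known vital status, or count the lost as alive. This stands in part: the SAP does not state in so many words that the living lost leave the mortality denominator. But it offers no other rule, and the natural alternative is biased in the opposite direction.

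A reader might also infer that the SAP plans a mortality comparison with inflated type I error. The document does not support that. It sets dropout equal across arms, and a null comparison is then unaffected. Swapping its own two dropout values between arms moves type I error only to 5.1%. The 2% vs 6% case goes beyond the planned 10-15% attrition, and d = 0.045 implies mortality above the expected 12-15%. Nor does ignoring follow-up time cost power in itself, as step 4 shows.

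Two further points stand. Section 1.13 would reveal unequal attrition, although it names no remedy for mortality. Log-rank and Cox replace one missingness assumption with another. The flexibility in 1.10.1 about realized distributions is no answer, since it concerns the choice of distribution and not censoring.

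**Conclusion.** The point holds in limited form. Read through its cross-references, the SAP tests mortality by a rule that keeps deaths and omits the living lost, and neither binary reading handles 10-15% loss without bias. Under the SAP's equal dropout the consequence is overstated levels, by roughly 1 to 1.5 points at the higher dropout rate, with no shift of a null comparison. A distorted comparison requires unequal dropout, which is an assumption: small at 3% vs 5% per quarter, and material mainly for power at the extreme 2% vs 6%. The sizes rest on constant quarterly rates, dropout unrelated to death and, except in step 6, a 12-month proportion in place of the full GEE. This is one secondary outcome, and the primary result is not affected. Changing it is worthwhile because the better analysis is standard and cheap.

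**What to change.** Redefine 1.9.1(i) as time from randomization to death from any cause, censored at the earlier of the date last known alive and 12 months, in all randomized participants. Report Kaplan-Meier 12-month risks by arm. Test with a site-stratified log-rank or Cox model, and feed the three-arm test and the three pairwise tests into the closed procedure that 1.10.1 already prescribes. Add to 1.10.1 that this outcome does not follow the binary rule.

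The cost is mostly SAP wording. The outcome leaves the common GEE code, and a last-known-alive date is needed for each participant. The SAP plans death narratives and disposition summaries but does not name that date, so its availability should be confirmed. Independent censoring remains an assumption and should be stated with the result, alongside the attrition comparison already planned in 1.13.
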